## **Statistical Analysis Plan**

The data was previously filtered (smoothing option) and windowed at 95% of test velocity. Data analysis was performed using the Acqknowledge 4.1 software. The mean and standard deviation (SD) of the PT assessments in the 5 repetitions of different muscles (IR and ER), actions (concentric and eccentric), and angular velocities (60°/s, 120°/s, and 180°/s) for both sides were calculated. Subsequently, the conventional concentric ER : concentric IR ratio and the functional eccentric ER : concentric IR ratio were verified for these three angular velocities.

All statistical analysis was carried out using IBM SPSS Statistics 27 software. Mean and SD were used for sample characterization. The Shapiro-Wilk test was used to verify the normality of the sample distribution. The homogeneity of variance between the three groups was verified for the sample characterization variables and the main outcome at T0, through the One-Way ANOVA or the Kruskal-Wallis tests. After this, an inter-group analysis in T0 and T1 and an intra-group analysis between T0 and T1 was made for dominant and non-dominant shoulders. For an inter-group analysis, the One-Way ANOVA or the Kruskal-Wallis tests were applied to compare differences between the three groups in T0 and T1. For an intra-group analysis, the Paired Sample T-test or the Wilcoxon test was applied to compare differences in each group between T0 and T1. A p-value  $\leq 0.05$  was considered as the level of significance for each difference in PT and ER:IR ratios.

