### *Intervention programs*

Twice a week, over 12-weeks, the two intervention groups carried out a strength training program with the 5 open kinetic chain exercises most often reported in the literature to prevent swimmer's shoulder: internal rotation (IR) at 90°, external rotation (ER) at 90°, scapular punches, T's, and Y's (Table

1). The weight program group performed these 5 exercises with two weights Domyos with 1, 2, 3, 4, or 5 kg (Fig. 1), and the elastic band program group with an elastic band Bodytone Power Band with 10, 15, 20, 25, or 30 kg (Fig. 2). The load used to perform the programs with elastic bands and weights was previously assessed and adjusted for each swimmer, corresponding to 75% of one repetition maximum (1 RM). After 6 weeks of program execution, each swimmer carried out another 1 RM test assessment, to verify the possibility of a load instrument progression.

[figure not shown]
Participants performed 2 sets of 10 valid repetitions in each exercise. The repetitions were considered valid when the swimmer reached the target range of motion (ROM) previously described for each exercise (Table 1). The concentric and eccentric phases of each exercise were performed for 5 seconds. A Tabata timer mobile application controlled this time. One minute of rest was preserved between different exercises and sets.

Programs were supervised by a sport physiotherapist independent of the study. Each athlete received individualized monitoring with a regular exercise technique correction in all sessions. The first session was in person and the following sessions have online monitoring through WhatsApp Messenger or Zoom Video Communications, Inc.

| Exercise  | Weight program                                                                                                                                                           | Elastic band program                                                                                                                                                                                                      |

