### *Outcomes and testing procedures*

Before (T0) and after 12-weeks (T1) of interventions and control procedures, concentric and eccentric peak torque (PT) of IR and ER of the dominant and non-dominant shoulder was performed through an isokinetic dynamometer Biodex System 3 (Biodex Medical Systems, New York), at 60°/s, 120°/s and 180°/s.

Previously to strength evaluations, each swimmer did a 10-minute warm-up of a general upper limb joint mobilization. The isokinetic dynamometer assessment was carried out with the swimmer in the supine position. Half of the swimmers started the assessment with the dominant shoulder, and the other half started with the non-dominant shoulder. Previously, this order was randomized for each swimmer. The upper extremity was positioned with the shoulder abducted to 90° and the elbow flexed to 90° so that the dynamometer's axis was aligned with the longitudinal axis of the humerus. The athlete's trunk and evaluated arm were stabilized using velcro straps to avoid compensatory movements (Fig. 3). Gravity correction was not used for this testing position because the ER and IR shoulder muscles moved with and against gravity as they applied force. Strength was tested through 145° of range of motion (ROM), between 80° of ER and 65° of IR, to obtain the PT variation in the maximum rotational ROM available. The tests started every time with the shoulder in 80° of ER. The concentric strength was tested first, followed by the eccentric strength test. The order of the angular velocity test was increased (60°/s-120°/s-180°/s) to preserve an ascending difficulty during the evaluations. A hard cushion deceleration control was selected to allow the subject the greatest availability of velocity attainment before deceleration. The procedure was explained to all athletes before the start of testing, with emphasis on exerting maximal effort within an individual's tolerance. After this, swimmers performed 3 submaximal trials to familiarize themselves with the ROM and the accommodating resistance of the dynamometer. Both concentric and eccentric tests at different velocities consisted of 5 maximal-effort reciprocal repetitions. Standardized verbal instructions and encouragement were given to all subjects. A minute rest period between different tests was preserved.

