### *Sample size*

The G\*power software (Franz Faul, Edgar Erdfelder, Axel Buchner, Universitat Kiel, Kiel, Germany, version 3.1.9.4) was used to calculate the sample size, considering an alpha level of 0.01, a power of 0.99, and an effect size (Cohen's *d*) of 2.81 based in a similar previous study. Thus, a minimum of 24 swimmers – 8 for different groups – was necessary.

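### Programme effects are tested separately by shoulder and, on the natural reading, by velocity, with no interaction test or pooled estimate, so a uniform effect of moderate size can look side- or speed-specific

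*Combined protocol and SAP*

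**What the plan says.** Outcomes and testing procedures provides for isokinetic measurement of "concentric and eccentric peak torque (PT) of IR and ER of the dominant and non-dominant shoulder" at 60, 120 and 180°/s, before and after the 12 weeks. The Statistical Analysis Plan adds two strength ratios at each velocity.

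For the tests, the Statistical Analysis Plan states that "an inter-group analysis in T0 and T1 and an intra-group analysis between T0 and T1 was made for dominant and non-dominant shoulders". Between groups it names one-way ANOVA or Kruskal-Wallis at T0 and at T1. Within each group it names the paired t-test or Wilcoxon test. Each difference is judged at 0.05.

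The split by shoulder is explicit. The split by velocity is not written in the test sentences, but it follows naturally from outcomes defined at each velocity combined with one-factor tests. The section names no side or velocity factor, no interaction, no repeated-measures or mixed model, and no pooling over cells.

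Both shoulders are trained. Under Intervention programs, "The weight program group performed these 5 exercises with two weights", and the exercise table describes the movements for both shoulders in both programmes.

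**The concern.** Both shoulders of a swimmer receive the same programme, so the natural first question is whether the programme changes a given strength measure overall. The plan has no analysis that answers it. It gives a set of separate verdicts instead.

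If one cell reaches 0.05 and its neighbour does not, that is not evidence that the effect differs between them; the difference has to be tested directly. Without such a test, a table with some significant and some non-significant cells invites the reading that a programme works on one side or at one speed only. Choosing between parametric and rank tests by a normality check can also put neighbouring cells on different tests, which makes their verdicts harder still to compare.

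This is separate from the number of tests. A multiplicity correction would control false positives but would not supply the missing comparison. The plan also leaves unused whatever precision six measures per swimmer offer over one.

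**Working it through.** **1. Counting the cells.** Peak torque: 2 muscles × 2 actions = 4 outcomes. With 2 ratios, that makes 6 outcomes. Each is measured in 2 shoulders × 3 velocities = 6 cells, giving 6 × 6 = 36 outcome cells. This means 36 between-group tests at T1, 36 at T0, and 36 × 3 groups = 108 within-group tests.

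**2. The plan's own figure.** Sample size gives an effect size "of 2.81 based in a similar previous study", "considering an alpha level of 0.01, a power of 0.99", and concludes that "a minimum of 24 swimmers – 8 for different groups – was necessary". For a two-sided two-sample t-test with d = 2.81 and n per group, the noncentrality is 2.81 × √(n/2). At n = 7 it is 5.26 and power is 0.972. At n = 8 it is 5.62 and power is 0.990. The stated 8 per group is reproduced (two-sided testing is assumed; the section does not say).

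**3. One cell at a smaller effect.** Assume both programmes shift a cell by 1.0 SD against control at T1. The group means are 0, 1 and 1, their average is 2/3, and the sum of squared deviations is 4/9 + 1/9 + 1/9 = 2/3. The noncentrality is λ = 8 × 2/3 = 5.33. One-way ANOVA at 0.05 with 2 and 21 degrees of freedom has power 0.47.

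**4. Six cells together.** The correlation ρ between a swimmer's cells is not in the documents, so a range is assumed. With equal correlation, the variance of the six-cell mean relative to one cell is (1 + 5ρ)/6, the standard error ratio is its square root, and λ becomes 5.33 divided by the variance ratio. Mixed verdicts (some of the six cells at p ≤ 0.05, others not) come from simulation of normal data, without T0 adjustment or dropout.

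| Uniform 1.0 SD, 8 per arm | ρ = 0.4 | ρ = 0.6 | ρ = 0.8 | ρ = 0.9 |
|---|---|---|---|---|
| Variance ratio | 0.50 | 0.67 | 0.83 | 0.92 |
| Standard error ratio | 0.71 | 0.82 | 0.91 | 0.96 |
| λ for six-cell mean | 10.7 | 8.0 | 6.4 | 5.8 |
| Power, one cell | 0.47 | 0.47 | 0.47 | 0.47 |
| Power, six-cell mean | 0.78 | 0.65 | 0.55 | 0.51 |
| Mixed verdicts | 81% | 68% | 49% | 35% |

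At a given velocity the two shoulders give different verdicts in about 38%, 32% and 22% of trials at ρ = 0.4, 0.6 and 0.8.

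**5. Dependence on effect size.** Mixed verdicts at T1 under a uniform effect:

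| d | ρ = 0.3 | ρ = 0.5 | ρ = 0.7 | ρ = 0.9 |
|---|---|---|---|---|
| 0.5 | 53% | 45% | 35% | 21% |
| 0.8 | 79% | 68% | 54% | 32% |
| 1.0 | 86% | 75% | 61% | 35% |
| 1.5 | 56% | 48% | 38% | 22% |
| 2.0 | 11% | 10% | 8% | 5% |
| 2.81 | 0.1% or less | 0.1% or less | 0.1% or less | 0.1% or less |

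The within-group paired tests behave alike. A standardised change of 0.8 gives mixed verdicts in 87%, 76%, 61% and 36% of trials at the same ρ values; 2.81 gives about 0%.

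**6. Which interaction test is safe.** With equal correlation between cells, a group-by-cell F test flags a uniform effect in about 5% of trials, as it should. If speeds within a shoulder correlate more strongly than values across shoulders, a model with only a swimmer random intercept uses the wrong error term for group × side. Simulated false-positive rates at a nominal 5% were about 16% (correlation 0.7 within a shoulder, 0.6 across), 30% (0.8/0.6 and 0.9/0.8) and 44% (0.9/0.6). A per-swimmer side difference compared between arms stayed near 5%.

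**7. What averaging costs.** If a 1.0 SD effect occurs at one velocity only, two of six cells move and the six-cell mean shifts by 1/3 SD. Its power is about 0.09 to 0.14, against about 0.47 in the affected cell.

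**The case against.** The strongest reply is that the plan was sized for a very large effect. If d = 2.81 held in every cell, nearly every cell would be significant and no patchwork would arise. That is correct, and it limits the point. But Sample size gives 2.81 as a single figure without naming the outcome, side, velocity or contrast, so it cannot be carried over to all 36 cells.

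Second, a reader might infer that the investigators intend to claim side- or speed-specific effects, or that a uniform effect is bound to look specific. The documents support neither. The Statistical Analysis Plan announces no such claims, and step 5 shows that the risk depends on effect size and correlation. What stands is that the plan produces separate verdicts by side with no safeguard against that reading.

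Third, the lost precision may be small. The arms mix sexes, and ages run from 16 to 35, so raw torque may correlate strongly across a swimmer's cells. At ρ = 0.9 the standard error falls by only 4%. This stands: the gain cannot be fixed from the documents.

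Fourth, treating each velocity as its own outcome is a legitimate choice, and an average can hide an effect confined to one velocity (step 7). This is why the cell results must stay in the report. It does not justify inferring a difference between cells that was never tested.

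**Conclusion.** The point holds as a risk. The plan has no group-by-side test, no group-by-velocity test and no pooled estimate, although each outcome is measured six times per swimmer at each assessment. Under an assumed uniform effect of 1.0 SD, mixed verdicts arise in about 35% to 81% of trials for ρ from 0.9 down to 0.4. They all but vanish at 2.81. The standard error of a six-cell mean is 0.71 to 0.96 of a single cell's for ρ from 0.4 to 0.9.

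The missing tests can be read directly from the text, apart from the split by velocity, which is inferred. The sizes rest on assumed effects and correlations, normal data, equal correlation between cells, no T0 adjustment and no dropout. The plan should be changed, but the documents do not show that any conclusion of the trial is wrong.

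**What to change.** In the Statistical Analysis Plan, for each of the four peak torques and two ratios:

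- **Overall effect.** Add a between-arm ANCOVA on each swimmer's six-cell mean at T1, adjusted for the six-cell mean at T0.
- **Interactions.** Test group × side on each swimmer's dominant-minus-non-dominant difference, and group × velocity on each swimmer's velocity contrasts, each adjusted for the matching T0 contrast. A mixed model is an alternative if it has an unstructured covariance, or swimmer-by-side and swimmer-by-velocity random effects. A random intercept alone is not enough (step 6).
- **Claims.** Make a side- or velocity-specific claim only if the matching test supports it. State that a non-significant interaction with 8 per arm does not prove uniformity.
- **Cells.** Keep the single-cell results as descriptive tables, because the average dilutes an effect confined to one velocity.

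The cost is some SAP text and a few analyses per outcome in the SPSS software already named; no new data are needed. Trial design describes the trial as completed, so if results have been seen, the additions should be labelled post hoc.

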## **Study Protocol**

### *Trial design*

A care provider and participants blinded, parallel, randomized controlled trial with three groups was completed from September 2022 to April 2023. This trial is reported according to the CONSORT 2010 checklist for randomized controlled trials. All procedures were approved by the Ethics Committee of the Polytechnic Institute of Coimbra (CEIPC 6/2022).

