### *Randomisation and blinding*

An initial screen survey was carried out on the two swimming teams before the sample selection. After the application of eligibility criteria, the eligible swimmers were divided into a weight program group, an elastic band program group, or a control group. The allocation to each group was performed through stratified randomization according to the team, sex, and main swimming style. This design was used to equate the possible effects of these three variables in results and was prepared with a computer random number generator by a member of the research team. Then, all swimmers carried out the T0 assessment moment through the isokinetic dynamometer. To minimize fatigue bias during the assessments, half of the swimmers started the evaluation with the dominant shoulder, and the other half started with the non-dominant shoulder. Previously, this order was randomized for each swimmer. After T0 moment, for 12-weeks the two experimental interventions were applied and supervised by a blinded sports physiotherapist external to the study, without knowledge of the previous procedures and the study objectives. It only explains in detail the interventions and the load that should be used by each athlete considering the 1RM test previously performed by a member of the research team. The participants were unaware of the existence of other sample groups. At the end of the 12-weeks, all swimmers who

completed the proposed interventions carried out the T1 strength assessment through the isokinetic dynamometer. All T0 assessment procedures were maintained in T1 moment.

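### No planned between-arm test of T1 adjusts for T0 or compares change, and no pairwise contrast is named; one post hoc T0-adjusted model would cheaply supply the three contrasts

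*Combined protocol and SAP*

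**What the plan says.** The Statistical Analysis Plan describes two analyses for each shoulder. Between arms, "the One-Way ANOVA or the Kruskal-Wallis tests were applied to compare differences between the three groups in T0 and T1". Within arms, "the Paired Sample T-test or the Wilcoxon test was applied to compare differences in each group between T0 and T1". The sentence before these assigns the comparison across time points to the intra-group analysis. Each difference is judged at 0.05. The plan names no covariate, no group-by-time term, no between-arm test of change and no pairwise procedure.

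Three statements under Randomisation and blinding bear on the point. "The allocation to each group was performed through stratified randomization according to the team, sex, and main swimming style", yet none of these factors enters a planned test. After allocation comes baseline testing: "Then, all swimmers carried out the T0 assessment moment through the isokinetic dynamometer". At the end, only swimmers who "completed the proposed interventions carried out the T1 strength assessment through the isokinetic dynamometer" supply a T1 value.

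The Sample size section works from "considering an alpha level of 0.01, a power of 0.99" and an effect size "of 2.81 based in a similar previous study", giving 8 swimmers per group and 24 in all. Trial design states that the trial is finished: "A care provider and participants blinded, parallel, randomized controlled trial with three groups was completed from September 2022 to April 2023".

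**The concern.** A trial with two programmes and a control is run to learn whether each programme differs from control and whether the programmes differ from each other. A significant three-group test at T1 says only that some group differs. The only p-values attached to a particular arm are the within-arm ones. A reader looking for the answer will be drawn to compare them, calling an arm effective because its change was significant and another ineffective because its change was not. That is not a comparison between arms.

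The T0 value of each swimmer is also already held. It would usually narrow the arm-versus-arm estimates, but the planned T1 test leaves it out.

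**Working it through.** **Inputs.** From the documents: 8 per group, alpha 0.01, power 0.99 and d = 2.81 (Sample size); 0.05 for each difference (Statistical Analysis Plan). Assumed, because the documents give no value: the T0-T1 correlation ρ, a 1 SD advantage of both programmes over control, complete data, and equal spread except where stated.

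**1. The plan's own figure.** The test family and sidedness are not stated. A two-sided two-sample t-test reproduces the number. With n = 8, the noncentrality is 2.81 × √(8/2) = 5.62 on 14 df and power is 0.990. With n = 7 it is 2.81 × √(7/2) = 5.26 on 12 df and power is 0.972. So 8 × 3 = 24. A one-sided t-test also gives 8; the one-way ANOVA versions tried with d spread over the three means give 7 or 9. The sizing is thus consistent with a two-group comparison, which the analysis plan never names.

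**2. What is missing.** Peak torque: 2 muscles × 2 actions × 3 velocities × 2 sides = 24. Ratios: 2 × 3 velocities × 2 sides = 12. That makes 36 outcomes and 3 × 36 = 108 pairwise comparisons without a planned estimate. This count needs no assumption about ρ.

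**3. What T0 would add.** With group means 1, 1 and 0 SD, λ = 8 × Σ(μ − mean)² = 8 × 2/3 = 5.33. T1 alone, F on 2 and 21 df: power 0.47. ANCOVA multiplies the residual variance by v = (1 − ρ²)(1 + 1/19), where 1/19 = 1/(24 − 3 − 2) is the average price of estimating the slope. Power then uses λ/v on 2 and 20 df. The 95% half-width of a contrast is 2.080 × √(2/8) = 1.04 SD for T1 alone and 2.086 × √(2v/8) for ANCOVA.

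| ρ | v | λ/v | Omnibus power, ANCOVA (T1 alone 0.47) | Half-width in SD, ANCOVA (T1 alone 1.04) |
|---|---|---|---|---|
| 0 | 1.053 | 5.07 | 0.45 | 1.07 |
| 0.3 | 0.958 | 5.57 | 0.49 | 1.02 |
| 0.5 | 0.789 | 6.76 | 0.57 | 0.93 |
| 0.7 | 0.537 | 9.93 | 0.75 | 0.76 |
| 0.8 | 0.379 | 14.07 | 0.88 | 0.64 |
| 0.9 | 0.200 | 26.67 | 0.99 | 0.47 |

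Power breaks even at ρ of about 0.24. If 2.81 is a between-group difference, λ = 2.81² × 5.33 = 42.1 and both tests exceed 0.999.

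**4. Error of the gated contrasts.** Simulated under no effect at ρ 0.5, 0.7 and 0.9, reading contrasts only after a significant omnibus test gives a false positive in 4.8% to 5.2% of trials per outcome. Three ungated contrasts give 11.5% to 12.2%.

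**5. Within-arm p-values.** Suppose every arm has the same true change and each paired test has power p. The arms disagree (some significant, some not) with probability 1 − p³ − (1 − p)³, which peaks at 1 − 0.125 − 0.125 = 0.75 when p = 0.5. In simulation with a common change of 0.3 or 0.5 SD at ρ 0.5, 0.7 and 0.9, the arms disagreed in roughly 30% to 70% of trials, although no arm differed from another.

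**6. Completers only.** An assumed loss pattern with no true effect: 10 per arm, the weakest 2 lost from each exercise arm and 2 at random from control. If weakness is judged on T0, the T1-only test rejects in 6% to 10% and ANCOVA in about 5%. If it is judged on T1, the figures are 13% to 14% and 8% to 11%.

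**7. Unequal spread.** With residual SDs of 1:1:2 across arms, pooled-variance 95% intervals miss the truth in about 8% of cases for contrasts with the wider arm and 1% for the other pair. Omnibus error is 6% to 7%. HC3 standard errors in the same setting bring the contrasts with the wider arm back to about 5%.

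**The case against.** The strongest reply is that nothing here is wrong. Randomisation makes a comparison at T1 a fair test, adjustment is an efficiency choice, and the size of the gain rests on a ρ and an effect that the documents do not give. At ρ = 0.3 power moves only from 0.47 to 0.49, below about 0.24 it falls, and at the documents' only effect size, read as between-group, there is nothing to gain. Adding 36 models and up to 108 contrasts to a finished trial also invites selective reading. All of this stands against presenting adjustment as a correction. None of it supplies the missing contrasts.

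The between-arm sentence might also be stretched to mean differences in change. The preceding sentence, which places the T0-to-T1 comparison within groups, makes that strained.

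Four stronger readings are tempting and are not supported:

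- A reader might infer that T0 plays no part in between-arm testing. It does: the groups are compared at T0, but only as a separate cross-sectional test.
- A reader might infer that the T1 test inflates false positives. That depends on whether completion is related to arm and strength. The documents neither show such a relation nor rule it out.
- A reader might infer that ANCOVA cures completers-only data. Step 6 shows that it can handle loss related to T0 but not loss related to T1 itself.
- A reader might infer that the plan bases efficacy on within-arm tests. It does not say so; it merely offers no other arm-specific p-value.

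**Conclusion.** The point holds as a cheap improvement, not as the repair of an invalid test. The firm part is the gap: the three comparisons that the design exists to make have no planned estimate, confidence interval or test on any of the 36 outcomes. That follows from the text alone.

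The gain from using T0 is conditional. With 8 completers per arm, equal spread and a 1 SD effect of both programmes, it ranges from a slight loss at ρ = 0 to roughly a doubling of omnibus power at 0.9 (0.47 to 0.99), with intervals less than half as wide (0.47 against 1.04 SD). The T1 omnibus test remains valid under randomisation if completion is unrelated to arm and strength, but T1 exists only for completers and numbers per arm are not given. T0 was also measured after allocation, and blinding is claimed only for care provider and participants, so T0 is not secured against knowledge of allocation by whoever tested.

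**What to change.** Keep the planned tests and add beside them, labelled post hoc because the trial is complete:

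- For each outcome, one ANCOVA of T1 on group with T0 as covariate.
- The three pairwise differences with 95% confidence intervals in original units, their p-values read only if the omnibus group test is significant.
- A check of residual spread across arms and, if it is unequal, heteroscedasticity-robust standard errors (for example HC3) for the contrasts.
- Within-arm changes as description only, with no efficacy claim.
- Numbers allocated and completing per arm, with a statement that adjustment can address loss related to T0 but not loss related to T1, and that T0 followed allocation.
- A statement that error across the 36 outcomes is not controlled: 36 × 0.05 = 1.8 significant omnibus tests are expected if nothing differs.

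Rank-based models and models that add team, sex and swimming style are optional.

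The cost is one re-run in the same software on data already held, one residual degree of freedom (21 to 20), a small loss of power if ρ is below about 0.24 (0.45 against 0.47 at ρ = 0), and the post hoc label. No new data are needed.

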### *Participants*

Swimmers were recruited from 2 national competitive teams in Portugal, affiliated with the Portuguese Swimming Federation during the 2022/2023 season. To be included in the sample, participants should be federated in the current season, aged between 16-35 years old, have a minimum of 5 years of experience in national competitions, and perform a minimum of 8 hours of weekly swimming training. Subjects who had performed at least 6 weeks of treatment such as physical therapy, injections, and medication, clinical situations such as a history of significant shoulder pain in the last 6 months, a history of traumatic shoulder injuries such as fractures, subluxations, cervical or thoracic conditions, previous shoulder surgeries, shoulder range of motion deficits, or neurological injuries, were excluded. All eligibility criteria were verified through an individual questionnaire before the sample selection. Each participant read and signed a written informed consent form based on the revised version of the 2013 Declaration of Helsinki. After being selected, all swimmers were weighed on a body composition scale Tanita RD-953, and measured using a stadiometer. The sample identity protection was preserved following the European Union General Data Protection Regulation – Regulation (EU) – 2016/679. This randomized controlled trial was conducted at the RoboCorp Laboratory at the Polytechnic Institute of Coimbra.

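### The only planned tests of T0–T1 change are uncontrolled within-arm tests at p ≤ 0.05, and the plan does not bar drawing programme conclusions from them

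*Combined protocol and SAP*

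**What the plan says.** The trial is a randomised, sham-controlled comparison in which swimmers were "divided into a weight program group, an elastic band program group, or a control group". The Statistical Analysis Plan sets out two families of tests.

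- **Between arms:** "the One-Way ANOVA or the Kruskal-Wallis tests were applied to compare differences between the three groups in T0 and T1". The sentence before it describes an inter-group analysis in T0 and T1, so this is read here as one comparison at each time point.
- **Within each arm:** "the Paired Sample T-test or the Wilcoxon test was applied to compare differences in each group between T0 and T1".

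One rule covers both: a p-value of at most 0.05 "was considered as the level of significance for each difference in PT and ER:IR ratios". The plan does not rank the two families, does not call the within-arm tests descriptive, and does not say which result would establish that a programme works. It lists no between-arm test of change: no change-score comparison, no ANCOVA and no group-by-time term.

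**The concern.** The purpose of a control arm is to show what would have happened without the programme. The within-arm tests leave that information out. Their null is zero T0–T1 change in one arm, and it can be false when neither programme does anything.

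The documents make a gain common to all arms plausible. Every swimmer had, at entry, to "perform a minimum of 8 hours of weekly swimming training" (Participants). All were tested twice with the same procedures, and before testing "swimmers performed 3 submaximal trials to familiarize themselves with the ROM and the accommodating resistance of the dynamometer" (Outcomes and testing procedures).

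A reader who asks whether a programme improved strength will look for a test of change, and the only one offered is the within-arm test. A programme could then be credited with a gain that the control arm also had. Comparing verdicts (programme arm significant, control arm not) does not repair this, because it sets two p-values side by side and not two changes.

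**Working it through.** **Inputs from the documents.** Three arms, two of them programmes. Planned size: "a minimum of 24 swimmers – 8 for different groups – was necessary" (Sample size). Analysis level 0.05 per difference; sidedness is not stated, so two-sided is assumed.

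**Assumptions.** The documents give neither the size of a shared gain nor the SD of change. The gain is written as dz = mean change ÷ SD of change and varied from 0 to 1.0. It is the same in all three arms, so the true programme effect is zero. Changes are taken as normal and arms as independent.

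**Step 1: the plan's own figure.** The Sample size section works by "considering an alpha level of 0.01, a power of 0.99, and an effect size" of d = 2.81. For a two-sided two-sample t-test the noncentrality is d × √(n/2).

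- n = 7 per arm: 2.81 × √3.5 = 5.26, power 0.972.
- n = 8 per arm: 2.81 × √4 = 5.62, power 0.990.

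So 8 per arm, and 3 × 8 = 24, is reproduced. The section does not name its test, but the figure fits a comparison of two groups at 0.01.

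**Step 2: within-arm test under a shared gain.** For the paired t-test with n = 8, df = 7 and the critical value is 2.365. The rejection probability q comes from the noncentral t with noncentrality dz × √8. Then:

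- at least one of two programme arms significant: 1 − (1 − q)²
- at least one programme arm significant and control not: (1 − q) × [1 − (1 − q)²]

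| Shared gain dz | dz × √8 | One programme arm (q) | At least one programme arm | At least one programme arm, control not |
|---|---|---|---|---|
| 0 | 0 | 5.0% | 9.8% | 9.3% |
| 0.2 | 0.57 | 7.8% | 15.0% | 13.9% |
| 0.3 | 0.85 | 11.4% | 21.5% | 19.1% |
| 0.5 | 1.41 | 23.2% | 41.0% | 31.5% |
| 0.75 | 2.12 | 44.9% | 69.6% | 38.4% |
| 1.0 | 2.83 | 68.1% | 89.8% | 28.7% |

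Worked line for dz = 0.5: q = 0.232; 1 − 0.768² = 0.410; 0.768 × 0.410 = 0.315.

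The first row shows that the paired test is correctly calibrated for its own null. The 9.8% and 9.3% in that row come from testing two programme arms, not from a shared gain. The last column peaks near 38% and then falls, because with a large gain the control arm becomes significant too.

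**Step 3: checks.** The Wilcoxon test behaves alike: by simulation, about 4%, 20% and 60% for one arm at dz = 0, 0.5 and 1.0. More swimmers per arm raise the rate: at dz = 0.5, q is 29% with 10 and 35% with 12.

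**Step 4: between-arm tests on the same data.** Simulation with 40,000 trials and an assumed T0–T1 correlation of 0.8 gave these rejection rates:

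| dz | ANOVA on T1 | ANOVA on change |
|---|---|---|
| 0 | 5.0% | 4.9% |
| 0.5 | 5.0% | 5.0% |
| 1.0 | 5.1% | 5.0% |

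A shared gain cancels between arms, so both keep their level.

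**Step 5: is the T1 ANOVA enough by itself?** Suppose both programmes end 1 SD above control (an assumption). The arm means are 0, 1, 1, with squared deviations from their mean summing to 4/9 + 1/9 + 1/9 = 2/3. The noncentrality is 8 × 2/3 = 5.33, and power at 0.05 on 2 and 21 df is 47%. With correlation 0.8 the variance of change is 2 × (1 − 0.8) = 0.4, so for change scores the noncentrality is 5.33 ÷ 0.4 = 13.33 and power is 87%. Removing the within-arm verdicts without adding a between-arm test of change would therefore leave a weak analysis.

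**The case against.** The strongest reply is that the plan nowhere says that a within-arm p-value shows a programme to work. The 0.05 rule defines when a difference is called significant, not when a programme is effective. Each paired test is valid for the question it asks, and a between-arm test that keeps its 5% level is already planned. This stands. A reader might infer from the shared threshold that the plan commits the trial to programme claims from within-arm results; the text does not support that. What remains is that it does not exclude such claims and offers no other test of change.

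Four further limits also stand.

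- **Size.** A reader might infer that the error is always far above 5%. It depends on a gain that the documents do not give, and at 0.2 SD of change it is only about 8%. The 8 hours of training is an entry criterion, not a record of the 12 weeks. Familiarisation also included a warm-up, an explanation and standardised instructions.
- **Ratios.** The rates apply to peak torque. A gain that raises external and internal rotation in the same proportion largely cancels in the ER:IR ratios.
- **Regression to the mean.** A reader might add this as a source of shared change. No eligibility criterion selects on peak torque, so the documents give no basis for it.
- **Multiplicity.** The 9% rate of a programme arm being significant and control not, at zero gain, belongs to testing two arms.

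**Conclusion.** The point holds as a gap in the plan, not as a proven error in a result. The within-arm tests are the only planned tests of change, they carry the same significance rule as the between-arm tests, and they cannot separate a programme from a gain that every arm shares. If a programme conclusion were drawn from one of them with 8 swimmers per arm and no programme effect, the false-positive rate for one arm would be about 8% to 68% for shared gains of 0.2 to 1.0 SD of change. Relying on significance in a programme arm and not in control would mislead in about 14% to 38% of trials over that range, against 9% with no shared gain. These figures rest on an assumed gain, normal changes and the planned minimum size. A conclusion that rests on the T1 comparison alone is not affected. Whether any reported claim rests on a within-arm p-value cannot be told from the documents.

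**What to change.** In the Statistical Analysis Plan:

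1. Base programme conclusions only on a between-arm comparison that uses the T0 value already collected: ANCOVA of T1 adjusted for T0, or change scores, with each programme contrasted with control.
2. Limit the p ≤ 0.05 rule to that comparison.
3. Report each arm's T0–T1 change descriptively, as a mean with a 95% confidence interval and no significance verdict.
4. State that no programme conclusion is drawn from a within-arm change, or from significance in one arm and not in another.

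The trial is described as completed, so the change applies to the analysis and the report, where it should be labelled as made after the data were collected. Any programme statement found to rest only on a within-arm p-value should be reworded. The cost is a small amount of extra analysis and some rewording, with no new measurements or swimmers. The downside is that fewer results can be called significant.
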